1.1 Part 1 Dose Escalation Segment

The primary objective of the Part 1 dose escalation segment is to determine the first cycle dose-limiting toxicities (DLTs) and the maximum tolerated dose (MTD) of TK216 administered intravenously via continuous infusion through a central venous catheter over seven days in patients with relapsed or refractory Ewing sarcoma (ES). (includes patients with Ewing sarcoma family of tumors-ESFT).

Secondary objectives of the dose escalation segment of the study are to assess:

- Safety profile of TK216 as characterized by Adverse Event (AE) type, severity, timing and relationship to study drug, as well as laboratory abnormalities in the first and subsequent treatment cycles
- Pharmacokinetics (PK) of TK216 in plasma
- Antitumor activity of TK216 as measured by Overall Response Rate (ORR), Duration of Response (DOR) as well as Progression-Free Survival (PFS) and Overall Survival (OS)
- Duration of Disease Control defined as first date of disease control identified (either CR, PR or SD) until the date of progression using RECIST, version 1.1
- Assay methods to detect EWS-FLI1 (or EWS-ERG and EWS-ets) molecular alterations and identify appropriate analytical cutoffs, and other relevant biomarker parameters
- Pharmacodynamics of TK216

1.2 Part 2 Schedule Escalation Segment

The primary objective of the Part 2 schedule escalation segment is to determine the first cycle dose-limiting toxicities (DLTs), maximum tolerated dose (MTD), and a biologically effective and recommended Phase 2 dose regimen (RP2D) of TK216 administered intravenously via continuous infusion through a central venous catheter in patients with relapsed or refractory Ewing sarcoma (ES). (includes patients with Ewing sarcoma family of tumors-ESFT).

Secondary objectives of the dose escalation segment of the study are to assess:

- Safety profile of TK216 alone and combined with vincristine as characterized by Adverse Event (AE) type, severity, timing and relationship to study drug, as well as laboratory abnormalities in the first and subsequent treatment cycles
- Pharmacokinetics (PK) of TK216 in plasma alone and when combined with vincristine

- Antitumor activity of TK216 as measured by Overall Response Rate (ORR), Duration of Response (DOR) as well as Progression-Free Survival (PFS) and Overall Survival (OS)
- Duration of Disease Control defined as first date of disease control identified (either CR, PR or SD) until the date of progression using RECIST, version 1.1
- Pharmacodynamics of TK216

1.3 Part 3 Expansion Segment

The primary objective of the Part 3 expansion segment is ORR defined as Complete Response (CR) and Partial Response (PR) of the RP2D regimen of TK216 administered intravenously via continuous infusion through a central venous catheter in patients with relapsed or refractory ES. (includes patients with Ewing sarcoma family of tumors-ESFT). The RP2D regimen may include use of vincristine, a standard therapy for Ewing sarcoma.

Secondary objectives of the Expansion Cohort segment of the study are to assess:

- Progression-Free Survival (PFS) defined as time from first dose of TK216 to tumor progression or death due to any cause
- Overall Survival (OS) defined as time from first dose of TK216 to death due to any cause
- Duration of response (DOR) as defined from the first date a response is identified (either CR or PR) until the date of disease progression
- Disease Control (DC) defined as the proportion of patients with a confirmed Complete Response (CR), Partial Response (PR) or Stable Disease (SD)
- Duration of Disease Control defined as first date of disease control identified (either CR, PR or SD) until the date of progression
- Safety and tolerability of TK216 alone and combined with vincristine as characterized by Adverse Event type, severity, timing and relationship to study drug, as well as laboratory abnormalities
- Exploratory biomarker development to enable prediction of drug toxicity, tumor response and the mechanism(s) of acquired study drug resistance.
- Pharmacodynamics of TK216 on molecular targets in surrogate tissue
- Pharmacokinetics (PK) of TK216 alone and when combined with vincristine

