8.9 Quality control

The sponsor, or its representative, will be responsible for implementing and maintaining quality assurance and quality control systems with written SOPs to ensure that the study is conducted and data are generated, documented (recorded), and reported in compliance with the protocol, cGCP and the applicable regulatory requirements.

9 Statistical Considerations

The clinical outcomes, laboratory, PK, and other safety data from all segments of the study will be analyzed descriptively. In addition to determining DLT and RP2D, results will be analyzed to

determine if a sufficient response signal and safety profile justifies further study. Descriptive statistical summaries for demographic and patient baseline characteristics will be produced, as well as statistical summaries of safety, efficacy and pharmacokinetic/pharmacodynamic results, where categories for statistical summaries will consist of the dose level and duration initially assigned for Parts 1 and 2 dose and schedule escalation, and the initial dose and duration in the Expansion Cohort (RP2D). In addition, exploratory analyses of both toxicity, response (ORR), Stable Disease (SD) and pharmacodynamic data will be performed for both the assigned and actual daily dose and duration of infusions, the actual number of days of treatment, and for cumulative exposure to study drug as expressed by the product sum of dose over time (area under the dose-time curve).

Disease Control Rate (DCR) defined as the proportion of patients with a confirmed Complete Response (CR), Partial Response (PR) or Stable Disease (SD) per RECIST v1.1 Duration of Response (DOR) defined from the first date a response is identified (either CR or PR) until the date of objective tumor progression per RECIST v1.1 Progression-Free Survival (PFS) defined as time from first dose of TK216 to objective tumor progression per RECIST v1.1 or death due to any cause, whichever occurs first.

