9.7 Efficacy

A modified intent to treat (mITT) approach will be used for efficacy analysis, in which the mITT population will consist of all patients who receive at least a partial dose of study therapy (i.e., any portion of the continuous infusion). Tumor response rates will be summarized by dose group and for all patients who receive the RP2D, including those from the dose and schedule escalation and expansion phases. Responses will be classified as CR, PR, SD or PD according to RECISTv.1.1 criteria. Summaries will be based on the best response recorded up until disease progression. Patients who discontinue prior to the first protocol-scheduled response assessment post first infusion will be considered as non-responders in the primary efficacy analysis. Objective tumor response (CR or PR) will also be summarized, as will PFS, OS, DCR and duration of response and DCR. Time to event data will be summarized by Kaplan-Meier methods, including 25th, 50th (median) and 75th percentiles with point estimates and two-sided 95% confidence intervals, as well as number and percent of censored observations.

10 Statistical analysis

The statistical analyses will be reported using summary tables, figures, and data listings. Continuous variables will be summarized with means, standard deviations, medians, minimums, and maximums. Categorical variables will be summarized by counts and by percentage of patients in corresponding categories. All raw data obtained from the case report forms as well as any derived data will be included in data listings. All analyses will be based on the Safety Population, which will include all patients who receive any amount of study drug.

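### DOR and duration of disease control end only at progression, so a death without documented progression is no event, although PFS beside them counts it

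*Combined protocol and SAP*

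**What the plan says.** **DOR.** Section 1.3 (Part 3) defines it "as defined from the first date a response is identified (either CR or PR) until the date of disease progression". The opening text of section 9, Statistical Considerations, has it run "from the first date a response is identified (either CR or PR) until the date of objective tumor progression per RECIST v1.1". Sections 1.1, 1.2 and 1.4 list DOR as an objective without saying what ends it, so the section 9 wording governs there too, including Part 4.

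**Duration of disease control.** Section 1.3 gives "Duration of Disease Control defined as first date of disease control identified (either CR, PR or SD) until the date of progression". Sections 1.1 and 1.2 define it as "first date of disease control identified (either CR, PR or SD) until the date of progression using RECIST, version 1.1".

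**PFS, for comparison.** The list in section 1.3 that holds the DOR definition also gives "Progression-Free Survival (PFS) defined as time from first dose of TK216 to tumor progression or death due to any cause". The section 9 paragraph that holds the DOR definition also gives "Progression-Free Survival (PFS) defined as time from first dose of TK216 to objective tumor progression per RECIST v1.1 or death due to any cause".

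**Analysis.** Section 9.7 states: "Time to event data will be summarized by Kaplan-Meier methods". It asks for quartiles with 95% confidence intervals, "as well as number and percent of censored observations". Sections 9, 9.7 and 10.6 give no censoring rule and do not mention a responder who dies with no progression on record.

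**The concern.** The plan names death where it means to count it, in PFS and OS. It leaves death out of the two duration endpoints defined alongside them. A statistician programming DOR from this text has no basis for treating death as an event.

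Such deaths are plausible here. The patients have relapsed or refractory disease, eligibility (section 3.1) asks for a life expectancy of only 3 months, and Part 4 scans (section 4.1.6.6) are about 8 weeks apart. A responder can die between two scans. If that death is censored, Kaplan-Meier treats the patient as someone who could still have progressed later, like a patient who is alive and under follow-up. The curve then describes a longer-lasting response than the patients had, and DOR and PFS disagree about the same patient.

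**Working it through.** **1. The definitions side by side**

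| Endpoint | Section | Starts | Ends | Death an event? |
|---|---|---|---|---|
| PFS | 1.3, 9 | First dose | Progression or death | Yes |
| OS | 1.3 | First dose | Death | Yes |
| DOR | 1.3, 9 | First CR or PR | Progression | Not named |
| Duration of disease control | 1.1, 1.2, 1.3 | First CR, PR or SD | Progression | Not named |

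**2. One patient traced through.** A patient has a first PR at one scan and dies before the next with no progression documented. PFS and OS each have an event on the date of death. DOR and duration of disease control have none. If the patient stays in the Kaplan-Meier analysis, it is as a censored observation on a date the plan does not give.

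**3. Size, as an illustration.** The plan gives no figure on this point, so there is none to reproduce. Assumptions:

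- The hazard of progression, a, and the hazard of death without documented progression, b, are both constant.
- Such deaths are censored on the date of death.
- f = b/(a+b) is the share of first events that are such deaths. The documents give no value for f.

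The median with death as an event is ln 2/(a+b). The median with death censored is ln 2/a. Their ratio is (a+b)/a = 1/(1-f).

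| f (assumed) | Ratio of medians | An assumed 6-month median becomes |
|---|---|---|
| 10% | 1/0.9 = 1.11 | 6.7 months |
| 20% | 1/0.8 = 1.25 | 7.5 months |
| 30% | 1/0.7 = 1.43 | 8.6 months |

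**4. In a small sample the shift is not smooth.** Take 4 responders, all with events at distinct times. With every event counted, the survival estimate is 0.75 and then 0.50, so the median is the 2nd time.

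- If the death at rank 1 is censored, the estimate is 2/3 at the 2nd time and 1/3 at the 3rd, so the median moves to the 3rd time.
- If the death at rank 2 is censored, the estimate is 0.75 and then 0.375 at the 3rd time, so the median again moves to the 3rd.
- Censoring only at rank 3 or 4 leaves the median at the 2nd time.

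The chance that the median moves is therefore 1-(1-f)^2, which is 19%, 36% and 51% at f = 10, 20 and 30%. Otherwise it does not change.

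**5. What does not depend on these definitions.** The rules in section 9.3 reproduce by exact binomial calculation. At least 4 of 18 gives a one-sided alpha of 0.098 and power of 0.835 (10% against 30%). At least 4 of 21 gives 0.019 and 0.808 (5% against 25%). Neither uses DOR or the Kaplan-Meier duration of disease control.

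**The case against.** **The endpoints carry little weight.** They are secondary, and section 9 says that clinical outcomes are analysed descriptively. PFS and OS count every death, and section 10 puts all raw and derived data into listings. With a handful of responders, a reader could find each death. This stands, and it limits the point to the correctness of two reported summaries.

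**Few patients may be affected.** Scans continue after discontinuation until progression, new therapy or withdrawal of consent (section 4.1.6.6). Contacts about every 3 months, with record review where applicable, follow progression and survival (section 4.2.7). A death counts here only if no progression was recorded by either route. This also stands: f is unknown, and the bias cannot be sized from the documents.

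**A progression-only duration could be deliberate.** It is a possible descriptive quantity, and nothing obliges DOR to use the same event as PFS. But the plan does not say that it intends this, and it does not say what happens to the deaths. Censoring them also requires that patients who died would otherwise have progressed at the same rate as those still followed, which is hard to defend in this population.

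**A stronger reading is tempting.** A reader might infer that the gap reaches the Part 3 rule in section 9.3, which counts response or stable disease of at least 3 months. The documents do not support this. That rule is a count of patients, it does not refer to the duration of disease control analysis, and its stated design reproduces. Section 9.3 does not say when the 3 months begin, but that is a separate clarification, and nothing in the documents shows that the rates were set from one starting point and counted from another.

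**Conclusion.** The point holds as an error in two endpoint definitions. DOR, including the Part 4 DOR that rests on section 9, and duration of disease control in Parts 1 to 3 do not count a death without documented progression. The planned Kaplan-Meier analysis has no rule for it. Followed literally, the plan can overstate durability.

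The textual gap is certain, but its size is not. The ratios of 1.11 to 1.43 rest on an assumed f of 10 to 30%, constant hazards and censoring at the date of death. With few responders, the median may not move at all. A reader might take these ratios as an estimate of bias in this trial, but the documents give no rate from which to make one.

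The primary objectives, both response rules and the sample sizes are unaffected. The change should be made because it corrects the summaries at almost no cost. It does not put the trial's conclusions on response in doubt.

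**What to change.** - **Sections 1.1, 1.2, 1.3 and 9:** end DOR at objective progression per RECIST v1.1 or death from any cause, whichever comes first, counted from the first documented CR or PR. End duration of disease control at the same event. Sections 1.1, 1.2 and 1.4, which list DOR without an end, then follow section 9.
- **Section 9.7:** state that patients with neither event are censored at their last adequate tumour assessment.

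**Cost:** wording only. Scans, progression and deaths are already collected under sections 4.1.6.6 and 4.2.7, so no visit or data item is added. The downside is that reported durations may be slightly shorter.

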1.4 Part 4: Dose and Schedule Evaluation Segment

Primary Objective:

The primary objective of the Part 4 dose and schedule evaluations segment is to assess ORR defined as Complete Response (CR) and Partial Response (PR), per RECIST v1.1, at a starting dose of 175 mg/m²/day of TK216 administered intravenously via continuous infusion over 28-days in patients with relapsed or refractory Ewing Sarcoma.

Secondary Objectives:

- Duration of response (DOR) per RECIST v1.1
- Disease control rate (DCR) per RECIST v1.1
- Progression free survival (PFS) per RECIST v1.1
- Overall survival (OS)
- Safety and tolerability of TK216 alone as characterized by AE type, severity, timing and relationship to study drug, as well as laboratory abnormalities

- Pharmacodynamics of TK216; Exploratory biomarker development to enable prediction of drug toxicity, tumor response and the mechanism(s) of acquired study drug resistance
- Pharmacokinetics of TK216 alone

2. Study Design

TK216-01 is a multicenter, open-label, Phase 1/2 study in which the safety and efficacy of TK216 will be evaluated in patients with relapsed or refractory ES (including patients with ESFT).

Once an appropriate patient has been identified, a 30-day screening period will begin to evaluate eligibility using the defined study inclusion and exclusion criteria.

The study will be executed in several Parts:

- **Part 1:** Dose Escalation Segment (Cohorts 1-6)
- **Part 2:** Schedule Escalation Segment (Cohorts 7-9)
- **Part 3:** Expansion Segment (Cohort 10)
- **Part 4:** Dose and Schedule Evaluation Segment (Cohort 11)

All patients will be treated until objective tumor progression per RECIST v1.1., withdrawal of consent, unacceptable toxicity, study termination by sponsor, or a maximum of 2-years. Patients may receive supportive care for bone marrow and/or gastrointestinal adverse events (e.g., with growth factors, antidiarrheals, antiemetics) and prophylaxis for established toxicities that are recurrent.

2.1 Drug Administration

TK216 will be administered intravenously by continuous infusion via a central venous catheter. Instructions on calculating the correct dose, as well as instructions on preparing the dosing solution will be provided in the Pharmacy Manual.

Vincristine is administered intravenously at a dose of 0.75 to 1.5 mg/m² up to a maximum dose of 2 mg.

2.2 Part 1 Dose Escalation Segment

The starting daily dose level in the dose escalation segment will be 18 mg/m²/day.

A “3+3” patient enrollment scheme will be followed during the dose escalation. This segment will be performed in sequential cohorts of patients receiving TK216 intravenously by continuous infusion via a central venous catheter. Cycles will consist of treatment for 7 consecutive days followed by a 14-day rest period (Cycle = 21 days). If 2 of 3 patients experience a first-cycle DLT then accrual to the cohort will cease. If a first-cycle DLT is seen in one of the 3 patients in a cohort, that cohort will enroll an additional 3 patients. The dose escalation will continue until a first cycle DLT has been observed in 2 of 6 or 2 of 3 patients. DLT is defined as an adverse event occurring during the first cycle that is at least possibly related to TK216 and meets the DLT definition. When 0 of 3, or 1 of 6 patients in a cohort experience DLT, the dose will be escalated in the subsequent cohort.

Dose escalation will begin with an accelerated phase in which the dose will be doubled in successive cohorts of 3 patients until 1 patient experiences a first-cycle DLT (as defined in Table 1); or 2 patients experience similar AEs that are greater than or equal to grade 2 severity (greater than or equal to grade 3 severity for hematological AEs) which occur during the first cycle. A toxicity that is clearly and incontrovertibly unrelated to TK216 may be excluded in consultation with the medical monitor.

Once this predetermined toxicity level has been encountered, subsequent cohorts will dose escalate in 50% increments following review of AEs and discussion with the investigators. The dose level for newly enrolled patients will be assigned by Oncernal Therapeutics, Inc. at the time of registration.

Table 1 Dose Limiting Toxicity – Part 1 Dose Escalation Segment

Category	Criteria
Hematology toxicities	
 Grade 4 neutropenia (absolute neutrophil count [ANC] < 500/mm³) lasting >7 days; Grade 4 anemia; Febrile neutropenia (ANC <1000/mm³ with a single temperature of > 38.3 °C or a sustained temperature of ≥ 38 °C for more than one hour); Grade ≥ 3 neutropenic infection (i.e., infection documented clinically or microbiologically with grade ≥ 3 neutropenia); Grade 4 thrombocytopenia (platelet count < 25,000/mm³); Grade 3 thrombocytopenia (platelet count < 50,000-25,000/mm³) lasting >7 days or associated with clinically significant bleeding.
Gastrointestinal toxicities	
 All ≥ Grade 4 vomiting or diarrhea; Grade 3 nausea or vomiting despite optimal antiemetic therapy that fails to recover to at least Grade 2 within 72 hours; Grade 3 diarrhea despite optimal management of the event that fails to recover to at least Grade 2 within 72 hours.
CNS toxicities	
 Grade ≥ 3
Other non-hematological toxicities	
 Grade ≥ 3; Grade 2 increase in AST/ALT in combination with a grade 2 increase in bilirubin; For patients with liver metastases with elevated liver transaminases at baseline (2.5-5x ULN), DLT shall be defined as a doubling of the baseline liver transaminase value(s); Toxicity of any grade that interrupts the first seven day infusion for ≥24 hours.
Failure to recover (except alopecia)	
 Failure to recover to Grade ≤ 2 toxicity or to baseline values after delaying the initiation of next cycle by a maximum of 21 days

Patients are eligible for DLT evaluation if they experience a DLT after receiving any amount of study drug or do not experience a DLT having taken a minimum of 85% of dose expected during the first cycle. Patients who do not fulfill these requirements and those who discontinue study participation prior to completing the first cycle will be replaced.

The MTD is the dose level at which 0 of 6 or 1 of 6 patients experience first-cycle DLT, and at least 2 of 3 or 2 of 6 patients experience first-cycle DLT at the next higher dose level. Effectively, the MTD is the highest dose associated with first-cycle DLT in < 33% of patients.

It is anticipated that 6 to 8 cohorts will be completed during the dose escalation segment of this trial. With the concurrence of the investigators and the study sponsor, further testing may be performed in up to 12 additional patients per dose level to refine the estimation of the MTD and RP2D at intermediate dose levels or to define a higher MTD and RP2D while using Cycle 1 primary supportive care prophylaxis (e.g., with growth factors, antidiarrheals, antiemetics) for bone marrow and/or gastrointestinal toxicities.

Additional cycles of therapy may be administered provided that the patient meets the following criteria on Day 1 of each cycle:

- ANC \geq 1,000/mm³
- Hemoglobin \geq 8.0 gm/dL (Blood transfusions are permitted.)
- Platelets \geq 50,000/mm³
- Non-hematologic toxicity recovered to \leq Grade 1 (or tolerable Grade 2)

Intra-patient dose escalation will be permitted during the dose escalation segment of this trial. Patients may have their dose of TK216 increased after they have completed 2 cycles of treatment at their assigned dose, assuming their initial dose was well tolerated and the subsequent cohort (at the next higher dose level) has been well tolerated through Cycle 1. At the investigator's discretion, the dose escalation can either take the form of an increase in daily dose with 7 days of dosing and 14 days of rest, or an increase of duration, with 14 days of dosing and 7 days of rest, but not both.

Other schedules of administration may be investigated after tolerability and PK data are acquired with this schedule.

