2.4 Part 3 Expansion Cohort

The expansion cohort segment of this study will consist of approximately 18 ES patients.

All patients in the expansion cohort will receive the RP2D of TK216 in conjunction with primary supportive care prophylaxis (e.g., with growth factors, antidiarrheals, antiemetics) for bone marrow and/or gastrointestinal toxicities. The first three patients will also receive vincristine intravenously on the first day of each treatment cycle, at a dose of 0.75 mg/m². If DLT (Table 2) is observed in 1 of 3 patients, an additional three patients will receive the same doses of TK216 and vincristine. If fewer than 1 of 6 patients experience DLT, then the remaining patients in the expansion cohort will receive the RP2D of TK216 plus vincristine given intravenously on the first day of each treatment cycle, at a dose of 1.5 mg/m² to a maximum of 2 mg/m² per dose. If DLT is observed in ≥2 of the first six

patients, then the dosing of vincristine and/or TK216 will be revised in consultation between the Investigators and the Sponsor.

If TK216 treatment has been well tolerated in Cycle 1 and 2, starting in Cycle 3 the duration of the TK216 infusion may be increased (e.g., from 14 to 17 or 14 to 24 days). If the longer infusion is well tolerated, the duration of the TK216 infusion may be increased further in subsequent cycles. There is no maximum treatment duration. If a longer infusion time is not well tolerated, the patient may remain on study, but receive a shorter duration of TK216 infusion in the next treatment cycle. The assessments noted for Days 8+/-1 and 15+/-1 in the Section 16.3 Schedule of Events (Schedule Escalation and Expansion Cohorts) should be performed every 7-8 days during longer infusions (Adverse events, Concomitant medications, Vital signs, Symptom driven physical exam, Hematology, Clinical chemistry, Coagulation, Urinalysis, and Plasma for PK assessment). A complete blood count (CBC with differential) should be obtained approximately half way between the weekly assessment at the study center or local laboratory.

In Part 3 dosing will follow the schedule for the RP2D selected. If TK216 treatment has been well tolerated in Cycles 1 and 2, starting in Cycle 3 the duration of the TK216 infusion may be increased, in consultation with the Sponsor.

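### In Parts 1 and 2 the stated accrual stop covers only 2 of the first 3 patients; after a second DLT in an expanded cohort, up to two more evaluable patients may start a regimen that can no longer pass

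*Combined protocol and SAP*

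**What the plan says.** Section 2.2 (Part 1) gives one rule that ends accrual to a cohort: "If 2 of 3 patients experience a first-cycle DLT then accrual to the cohort will cease". For one DLT in three it says: "If a first-cycle DLT is seen in one of the 3 patients in a cohort, that cohort will enroll an additional 3 patients". Nothing makes the second trio depend on what happens in patients 4 and 5.

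The surrounding rules in 2.2 are:

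- Escalate: "When 0 of 3, or 1 of 6 patients in a cohort experience DLT, the dose will be escalated in the subsequent cohort".
- End of escalation: "The dose escalation will continue until a first cycle DLT has been observed in 2 of 6 or 2 of 3 patients".
- MTD, the level itself: "The MTD is the dose level at which 0 of 6 or 1 of 6 patients experience first-cycle DLT".
- MTD, the level above: "at least 2 of 3 or 2 of 6 patients experience first-cycle DLT at the next higher dose level".
- MTD in words: "Effectively, the MTD is the highest dose associated with first-cycle DLT in < 33% of patients".

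Section 2.3 (Part 2) repeats the accrual stop at two of three, the unconditional second trio and the same escalation rule. Its worked illustration chooses the next cohort's regimen on two or more DLTs, without a denominator, and does not mention accrual to the cohort that is still open. In both parts, patients not evaluable for DLT are replaced, with no exception once two DLTs have occurred.

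Section 2.4 (Part 3) has a similar run-in: "If DLT (Table 2) is observed in 1 of 3 patients, an additional three patients will receive the same doses of TK216 and vincristine". It contains no accrual stop at two of three. At two or more DLTs in the first six, dosing is revised by consultation.

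**The concern.** Once an expanded cohort has two DLTs it cannot finish at 1 of 6. It will finish at 2, 3 or 4 of 6, and each of those counts gives the same answer under the escalation and MTD rules. Patients still to be enrolled would therefore be exposed to a regimen that has already failed the plan's own criterion, and their outcomes could not alter that decision. Section 3.1 admits patients from age 12 in Cohorts 2 to 5 and from age 10 in Cohorts 6 to 10, so some of them could be minors.

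**Working it through.** **Inputs.** The accrual, escalation and MTD rules are those of 2.2 and 2.3. The table of escalation probabilities is in 9.3. One assumption is not in the documents: patients 4, 5 and 6 start one after another, with each outcome known before the next start. DLT outcomes are taken as independent with a common probability p.

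**1. Reproduce the plan's table.** A cohort passes with 0 of 3, or with 1 of 3 followed by 0 of 3:

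P(escalate) = (1−p)³ + 3p(1−p)² × (1−p)³ = (1−p)³ + 3p(1−p)⁵.

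At p = 0.3 this is 0.343 + 0.9 × 0.16807 = 0.494. Over p = 0.05, 0.1, 0.2, 0.3, 0.4, 0.5, 0.6, 0.7 it gives 0.9734, 0.9061, 0.7086, 0.4943, 0.3093, 0.1719, 0.0824, 0.0321. All eight agree with 9.3 to two decimals (0.97, 0.91, 0.71, 0.49, 0.31, 0.17, 0.08, 0.03).

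**2. Starts after the decision is settled, given one DLT in the first three.**

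- DLT in patient 4 (probability p): two patients still to start.
- No DLT in patient 4, DLT in patient 5 (probability (1−p)p): one still to start.
- Second DLT first seen in patient 6, or not at all: none.

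Expected excess starts per expanded cohort = 2p + p(1−p). Chance of at least one = 1 − (1−p)². Expected DLTs among the excess starts = p × (2p + p(1−p)).

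**3. Per cohort opened.** A cohort expands with probability 3p(1−p)². Multiply by this.

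| True DLT rate | Excess starts per expanded cohort | At least one | DLTs among them | P(cohort expands) | Excess starts per cohort opened |
|---|---|---|---|---|---|
| 30% | 0.60 + 0.21 = 0.81 | 0.51 | 0.243 | 0.441 | 0.36 |
| 40% | 0.80 + 0.24 = 1.04 | 0.64 | 0.416 | 0.432 | 0.45 |
| 50% | 1.00 + 0.25 = 1.25 | 0.75 | 0.625 | 0.375 | 0.47 |

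**4. Effect of a stop at the second DLT.** An expanded cohort passes only if patients 4 to 6 have no DLT, and then the stop is never triggered. Enumerating all 2⁶ outcome sequences with the stop in place returns the eight escalation probabilities in step 1 unchanged.

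**5. Sensitivity to the assumption.** If patients 4 to 6 start together, no start is avoidable. Partial staggering falls between zero and the table. Two is the maximum for evaluable patients; because non-evaluable patients are replaced without exception, the literal text could produce more than two starts.

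**The case against.** The strongest reply is that the stop is implied. Section 2.2 continues escalation only until two DLTs in three or in six, and the sponsor assigns the dose level at registration, so patients 5 and 6 need not enter a failed level. This is a fair account of how a careful team would act, and the documents do not show that anyone would be enrolled in this way. But the first sentence governs movement between levels, and assignment at registration permits a halt without requiring one. The explicit accrual stop is written for two of three only.

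Three stronger readings are tempting and are not supported:

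- **That a cohort halted at 2 of 4 or 2 of 5 would not count as a failed level.** A reader might infer this from the MTD definition, which names only two of three or two of six. But 2 of 4 is 50% and 2 of 5 is 40%, and both fail the below-33% sentence in 2.2. In Part 2 the two-or-more wording already covers them. The wording is uneven, but the classification is not lost.
- **That the same defect and the same remedy apply to Part 3.** Section 2.4 has no two-of-three stop to amend. Its condition for proceeding is fewer than one DLT in six, and two or more lead to a consultation on both drugs, where 2 of 6 and 4 of 6 may matter differently. A sentence closing accrual could shut the whole expansion cohort of about 18.
- **That the extra patients contribute nothing.** They cannot change the escalate or MTD answer, but they add descriptive safety data. In Part 2 the next dose and schedule are chosen after evaluation of first-cycle results. Sections 2.2 and 2.3 separately allow up to 12 further patients per dose level by agreement.

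It is also fair to say that the per-expanded-cohort figures are a best case for the fix, and that the per-cohort-opened figures are less than half as large.

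**Conclusion.** The point holds for Parts 1 and 2. The text states an accrual stop for the first three patients and omits it for the expanded six, although the plan's own pass rule makes a second DLT decisive in both. At true DLT rates of 30% to 50%, the literal reading costs on average 0.81 to 1.25 patients per expanded cohort, or about 0.36 to 0.47 per cohort opened. These sizes rest on fully staggered starts and independent outcomes. No figure in 9.3 is wrong.

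For Part 3 only a narrower statement is justified. Section 2.4 does not say what happens to enrolment at the current doses between a second DLT and the consultation. Its two thresholds also leave exactly one DLT in six under neither rule, and a run-in that has expanded after one DLT can never have fewer than one.

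The documents do not say whether Parts 1 and 2 are still enrolling. If they have closed, the remaining value lies in recording how any second DLT in an expanded cohort was handled.

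**What to change.** In 2.2 and 2.3, reconcile the accrual sentence with the plan's own boundary: accrual to a cohort closes once a second first-cycle DLT is observed, whether among the first three or the expanded six. In 2.2, align the two-of-three or two-of-six wording, both where escalation ends and in the MTD definition, with the two-or-more wording of 2.3. State whether patients 4 to 6 are staggered, since the amount saved depends on it.

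In 2.4, do not insert an accrual stop. State what happens to enrolment at the current doses between a second DLT and the consultation, and reconcile the fewer-than-one-of-six and two-or-more-of-six rules.

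The cost is a few sentences. The escalation rule and the 9.3 table are unchanged. The one loss is fewer patients from whom to describe the DLT rate at a failed level.
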